11.1.1.1 STUDY OVERVIEW

Brief Description of the Purpose of the Study – This is a pilot and feasibility study featuring a randomized controlled trial of an adapted telehealth-delivered Diabetes Prevention Program augmented by Community Health Workers plus/minus pharmacotherapy (metformin). The intervention and measurement protocols pose minimal risk to participants given our plans for the protection of research volunteers. We anticipate no major adverse events or serious adverse events except for nausea in some patients taking metformin. The data and safety monitoring plan for this trial focuses on close monitoring by the PIs and research staff in conjunction with a data safety and monitoring board (DSMB), along with prompt reporting of excessive adverse events and any serious adverse events to the NIH and to the IRB at UAB. The study procedures pose little to no risk for human subjects. However, a medical monitor (MM) will review the protocol and monitor conduct of this study.

Adherence Statement - The Data Safety Monitoring Plan (DSMP) outlined below will adhere to the protocol approved by the UAB IRB

11.1.1.2 CONFIDENTIALITY

A. Protection of Subject Privacy – All volunteers are assured of their confidentiality both verbally and in the informed consent forms. The facilities are strictly limited to the staff of the research institution, clinics and to research volunteers. This is accomplished by a variety of stringent security measures. All medical records are stored in locked areas. Access to these areas is limited to the clinical support staff and the PI of the study. Volunteers' medical records are filed according to ID numbers. All forms on the chart, with the exception of consent form, display only the ID number.

B. Database Protection – Electronic data storage is similarly restricted with only the data management staff having access to databases containing confidential clinical records, i.e. those containing name or other identifying information.

C. Confidentiality during AE Reporting – Adverse events will be reported to the study PI, Project Manager, Medical Monitor, DSMB and Chair of the IRB throughout the trial. Adverse event data will be analyzed quarterly, but serious or life-threatening adverse events require immediate reporting and follow-up. AE reports and quarterly summaries will not include subject-identifiable material. Each will include the identification code only.

11.1.1.3 ADVERSE EVENT INFORMATION

A. Definition - An adverse event (AE) is any untoward medical occurrence in a subject temporally associated with participation in the clinical study. An adverse finding can include a sign, symptom, abnormal assessment (laboratory test value, vital signs, electrocardiogram finding, etc.) or any combination of these. A Serious Adverse Event (SAE) is any adverse event that results in one or more of the following outcomes: death; a life-threatening event; inpatient hospitalization or prolongation of existing hospitalization; a persistent or significant disability/incapacity; a congenital anomaly or birth defect; important medical event based upon appropriate medical judgment.

B. Classification of AE Severity – AEs will be labeled according to severity which is based on their impact on the patient. An AE will be termed 'mild' if it does not have a major impact on the patient, 'moderate' if it causes the patient some minor inconvenience and 'severe' if it causes a substantial disruption to the patient's wellbeing. The Site Staff for this trial will be responsible for determining the 'severity' of AEs. Site Staff will also make an initial evaluation of the 'seriousness' of the AE in order to determine if the AE needs to be elevated to the MM immediately upon discovery. The MM will make the final and official determination of the 'seriousness' of an AE. We anticipate most adverse events will be "mild" and the participant will be able to resume daily activities within a day or two of reporting the event.

C. AE Attribution Scale – AEs will be categorized according to the likelihood that they are related to the study intervention. Specifically, they will be labeled as either related or unrelated to the study intervention, and this relationship will be confirmed by the Medical Monitoring Team (MMT) for this trial.

D. Expected Risks – This study does not involve major risk to screeners and trial participants. Efforts to minimize the potential risks of the assessment methods and outcome variables include frequent monitoring by the investigators to assure that no volunteer suffers any adverse effects from participating in the research. The expectedness of an AE will be determined by the Medical Monitoring Team (MMT).

The study procedures include:

- a) Body height and weight. There is minimal risk to participants from these measurements.
- b) Finger stick blood sample. There is the possibility of pain and bruising on the finger where the finger prick is made. Aseptic (sterile) technique and trained personnel minimize these risks.
- c) Diet. Patients may modify their diet based on intervention recommendations that is safe for humans and has been tested repeatedly in clinical trials.
- d) Increased physical activity. Patients in the intervention arm will be counseled to increase physical activity to levels that are consistent with the recommendations for US adults (30 minutes of moderate intensity activity per day). There is the possibility of adverse events such as minor musculoskeletal problems, but risk is minimized by excluding potential participants with contraindications to exercise. Considering these types of events are expected in this trial they will not be recorded or reported unless they meet the definition of a Serious Adverse Event. Patients are counseled to secure physician approval before beginning any new exercise plan.
- e) Gastrointestinal (GI) upset from taking metformin. For patients enrolled in the lifestyle plus metformin recommendations, we will ask patients to monitor their symptoms. Metformin is recommended by the American Diabetes Association for the prevention of diabetes among those at high-risk. To minimize nausea and GI upset, in the Orientation for providers and provider handout on metformin therapy recommendations, materials will describe how to start patients at low dose of 250mg daily and increase to 250mg twice daily after 2 weeks as tolerated. Enrolled participants who do not tolerate metformin (e.g., due to gastrointestinal symptoms) will continue to be followed for 12 months on an intent-to-treat basis. This is a minor risk and is reversible.

E. SAE Reporting - SAEs that are unanticipated, serious, and possibly related to the study intervention will be reported to the Medical Monitoring Team and the UAB IRB in accordance with requirements. Anticipated SAEs or those unrelated to the study intervention will be reported to the same individuals/entities in accordance with requirements. Clinics will be required to report to the Medical Monitoring Team adverse events that are serious or in doubt about being serious within 24 hours of discovery. Other adverse events that are not serious but are unexpected and are associated with the study procedures will be reported within 10 days.

Data Quality and Safety Review Plan and Monitoring

A. Data Quality and Management – A Medical Monitor (MM) will be selected and will meet regularly throughout the study period. The MM will meet twice per year throughout the trial, and will be convened for a first meeting prior to recruitment of patients. A minimum of 1 meeting each year will be conducted. Prior to the start of recruitment the MM will give formal approval of the study protocol and informed consent.

Major Responsibilities of MM:

1. Sign and abide by a statement of confidentiality
2. Disclose any actual or potential conflicts of interest
4. Be familiar with the research protocol and plans for safety monitoring
5. Oversee safety of participants, which will include review of interim/cumulative data for evidence of study-related adverse events (including serious adverse events)
6. Review data quality, completeness, and timeliness (including recruitment)
7. Review adherence to the protocol
8. Review factors that might affect the study outcome or compromise the confidentiality of the trial data (such as protocol violations, unmasking, etc.)
9. Review reports of related studies, as appropriate

10. Review major proposed protocol modifications

Reports: Following each meeting, the MM will provide written documentation regarding findings for the study as a whole and any relevant recommendations related to continuing, changing, or terminating the study. All MM recommendations will be submitted to the Principal Investigator and/or his designee.

The MM will monitor and review recruitment, adverse events, data quality, outcome data, and overall awardee performance. The PI and Project Manager will regularly review all data collection forms and source documents on an ongoing basis for data completeness, accuracy, and compliance with the protocol. A statement reflecting the results of the review and describing any protocol deviations will be sent to the IRB in an annual report (non-competing continuation).

B. Subject Accrual and Compliance - Review of subject accrual, adherence to inclusion / exclusion criteria, and rates of study completion will occur quarterly. These data will be reviewed by the study PI and Medical Monitor.

C. Out of Range Data – Laboratory and physical measurement reports will be reviewed weekly by the Medical Monitoring Team for the study. Out-of-range values for A1c will be reported to the patient as soon as possible so that they can follow up with their PCP.

Measure	Alert Value	Notify Patient	Notify PCP
A1c	≥6.5%	At Visit or Within 1 week or sooner as indicated by exact value and judgment of Medical Monitor	Provide letter to PCP with A1c value and instruct the patient to notify their PCP within 1 week or sooner as indicated by exact value and judgment of Medical Monitor

D. Stopping Rules - This study will be stopped prior to its completion if: (1) adverse effects that significantly impact the risk-benefit ratio have been observed; (2) study recruitment or retention becomes futile; (3) any new information becomes available during the trial that necessitates stopping the trial; and (5) other situations occur that might warrant stopping the trial. Because one of the most likely reasons for stopping the trial is the inability to recruit the study sample, the PI will include an assessment of recruitment futility in the annual progress report to funder and will consult with a biostatistician if necessary to assess the impact of significant data loss due to problems in recruitment, retention or data collection.

E. Safety Review Plan - The PI will monitor the progress of the study weekly, including reasons for attrition and whether all participants met entry criteria. Further, progress and safety will be reviewed quarterly. These progress reports will include information on recruitment, retention/attrition, and AEs and will be provided to the Medical Monitor quarterly. The Medical Monitor will also receive a yearly report that details data relevant to the possible early termination of the study. We will establish a DSMB and we will provide reports to the DSMB prior to each meeting on adverse events and recruitment.

F. Informed Consent

Patients are volunteers that will be recruited through primary care clinics. The UAB's Institutional Review Board (IRB) as well as the IRBs of the partner institutions will approve the study protocol and all consent forms. Trained recruiters will obtain informed consent from all participants as well as HIPAA authorization. All questions and concerns are clarified before any forms are signed.

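### Sites are told not to record non-serious exercise-related events, which conflicts with the plan's own rules on who judges expectedness and seriousness and on what the monitors review

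*Combined protocol and SAP*

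**What the plan says.** Item d on increased physical activity appears with the same wording in section 10.1 (Potential Risks) and in section 11.1.1.3 (part D, Expected Risks). It describes the class by example: "There is the possibility of adverse events such as minor musculoskeletal problems". It then gives the instruction: "these types of events are expected in this trial they will not be recorded or reported unless they meet the definition", the definition meant being the one for serious adverse events.

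Elsewhere the plan assigns the decisions on adverse events as follows.

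- **Seriousness** (11.1.1.3, part B): "Site Staff will also make an initial evaluation of the" seriousness of an event, so that it can be escalated at once if needed. "The MM will make the final and official determination of the" seriousness.
- **Severity** (part B): rated by site staff as mild, moderate or severe.
- **Relatedness** (part C): confirmed by the Medical Monitoring Team.
- **Expectedness** (part D, opening paragraph): "The expectedness of an AE will be determined by the Medical Monitoring Team (MMT").

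On review, section 11.1.1.2 (item C) sends adverse events to the investigator, the Medical Monitor, the DSMB and the IRB chair, and adds: "Adverse event data will be analyzed quarterly". The monitoring plan at the end of 11.1.1.3 makes the Medical Monitor responsible for reviewing cumulative data on study-related adverse events, serious ones included. It also promises quarterly reports containing adverse events to the Medical Monitor and adverse event reports to the DSMB before each meeting.

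**The concern.** Item d settles in advance, for a whole class of events, two questions that the same section reserves for the monitors. A site that regards an exercise-related event as expected and non-serious is told to leave no record of it. No monitor can then confirm or correct that view, and the event cannot appear in any later summary.

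At stake is the completeness of the safety data for physical activity counselling, the part of the programme that every participant receives. This is a pilot meant to inform a larger trial. It would finish without a count of a harm that the protocol itself names and expects.

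**Working it through.** The point concerns recording rules. The plan gives no figure to reproduce and no arithmetic applies, so the check follows one event through the text.

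1. **Is the event an adverse event?** Yes. The definition in 11.1.1.3, part A, takes in any untoward medical occurrence that is associated in time with participation. A non-serious exercise injury falls inside it.

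2. **What should happen under parts B to D?** Site staff rate severity and make a first judgement of seriousness. The Medical Monitor makes the final judgement of seriousness. The Medical Monitoring Team confirms relatedness and decides expectedness. All of this requires the event to be on record.

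3. **What happens under item d?** If the site judges that the event does not meet the SAE definition, nothing is recorded. The site's first judgement of seriousness becomes the last one, and the Medical Monitoring Team rules on neither expectedness nor relatedness.

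4. **Does part E restore the event?** Part E has two routes. Events that are serious, or in doubt about being serious, go to the Medical Monitoring Team within 24 hours. Non-serious events that are unexpected and associated with study procedures are reported within 10 days. A non-serious event already labelled expected fits neither. The general rule in 11.1.1.2 would have carried it into the quarterly analysis, but item d removes it before that point.

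5. **Does any other data source restore it?** The change-in-health questionnaire at 6 and 12 months and the chart abstraction (both section 7) might pick up some of these events. Neither is linked to adverse event reporting or to the monitors.

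6. **How wide is the class?** The one example is of minor problems, but it is introduced as an example and no list follows. The only stated filter is seriousness. Severity is a separate scale in part B, on which an event causing some minor inconvenience already counts as moderate. A non-serious event that site staff would rate above mild could therefore go unrecorded.

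7. **Which arms does it cover?** Item d speaks of a single intervention arm. Sections 3 and 6.1.1 give the lifestyle programme, including the activity advice, to all participants in both arms. The wording does not match the design.

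**Result.** For events that the site is confident are non-serious, item d cannot be followed together with 11.1.1.2 item C and parts B to D of 11.1.1.3. If item d is followed, these events are absent from the quarterly summaries, the Medical Monitor's cumulative review and the DSMB reports.

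**The case against.** The best defence is that this is an open and limited choice in a study that the plan describes as minimal risk. The example is confined to minor problems. Site triage of seriousness is the plan's design for every event. The Medical Monitor approves the protocol before recruitment and so knows of the exemption. The pilot's stated targets are feasibility, weight and HbA1c, not exercise injury rates.

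Part of this stands, and it rules out several stronger readings that a reader might infer.

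- **That alarming events, such as chest pain during exercise, would go unrecorded.** The SAE definition includes important medical events on medical judgement. Events of doubtful seriousness go to the Medical Monitoring Team within 24 hours, and unexpected procedure-related events are reported within 10 days. The gap is limited to events that the site is confident are non-serious.
- **That the first stopping rule is disabled.** That rule refers to "adverse effects that significantly impact the risk-benefit ratio have been observed". Nothing in the documents suggests that non-serious musculoskeletal complaints alone would reach that level, and the investigator also reviews reasons for attrition weekly. The link is weak.
- **That recording would differ by arm and bias the comparison.** Section 6.1 describes both conditions as intervention arms and gives both the same programme. Differential recording is possible under the loose wording but is not shown.
- **That this is the most common harm in the trial.** The documents rank no frequencies, and the study overview in 11.1.1.1 singles out nausea on metformin.

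The defence does not remove the contradiction. No section says that protocol approval replaces the Medical Monitoring Team's decision on the expectedness of an individual event. Nor does any section except these events from the quarterly analysis. Limiting the burden of minor events is a reason not to expedite them; it does not require leaving them unrecorded.

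**Conclusion.** The point holds as a conflict between the recording rule in item d and the plan's own arrangements for classifying and reviewing adverse events. By rule, the loss is complete for exercise-related events that the site is confident are non-serious, in up to 100 participants over 12 months. How many events that means cannot be estimated, because the documents give no expected rate.

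The damage is mainly to the absolute safety and feasibility data that the pilot should hand to the larger trial. The documents do not support a claim that the between-arm comparison, the weight and HbA1c results or the handling of serious events is compromised.

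The conclusion assumes that sites follow item d as written and that no procedure outside these documents brings the events back into the adverse event record. It should be corrected, and the correction is small.

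**What to change.** In item d of both section 10.1 and section 11.1.1.3:

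- Replace the instruction not to record with a statement that these events are entered in REDCap with severity and relatedness, and are included in the quarterly summaries to the Medical Monitor and in the DSMB reports.
- State that no expedited reporting applies beyond what part E of 11.1.1.3 already requires. No new expedited category is needed.
- Replace the reference to patients in the intervention arm with participants in both arms.

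The decisions on expectedness, relatedness and final seriousness stay where parts B to D already place them.

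The cost is a wording change in two places, a short data entry per event and a somewhat longer quarterly listing. Design, sample size and treatment are unaffected.

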11.2 INCLUSION OF WOMEN AND MINORITIES

Inclusion of Women - Women will be included in this intervention with equal probability as men as the inclusion criteria include both men and women.

Inclusion of Minorities - We have selected clinics with a high proportion of patients with low socio-economic status and African Americans; however, our inclusion criteria do not specify any specific ethnicity. Thus, we anticipate that the socio-demographic distribution of patients will follow closely the patient population in selected clinics.

11.3 INCLUSION OF CHILDREN

The focus of the Funding Announcement under which this study was funded is on diabetes prevention in adults therefore the patients in this study are mainly adults (19 - 65 years of age). The evidence-based intervention for lifestyle modification was trialed in adults and the treatment of childhood obesity and prevention of type 2 diabetes is beyond the scope of this intervention.

12 POWER AND SAMPLE SIZE

For this pilot study, the importance of sample size lies in establishing feasibility and the precision of estimated changes which will inform the design of future studies. We will recruit 25 participants at each of four clinics (2 clinics for each intervention), for a total of 50 per intervention, or 40 per intervention allowing for 20% attrition. The clustering of patients within practices, as measured by the intra-class correlation (ICC) may result in a reduced effective sample size. In considering the impact of the ICC, we relied on the ENCOURAGE study⁴⁹, our previous practice-randomized trial of diabetics in the Black Belt. ICCs were essentially negligible in that study; estimated ICCs were <0.01 and not statistically significant. The impact of the ICC is quantified by a design factor (D) defined as $1+ICC \times (N-1)$ where N is the number of subjects per cluster. However, with an ICC of 0.01, the effective sample sizes per group are 40 (without attrition, D=1.24) and 33 (allowing for 20% attrition, D=1.19). This range of sample sizes will allow us to use to estimate changes in body weight with 95% confidence intervals that are ± 0.28 standard deviations to ± 0.35 standard deviations.

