5 RANDOMIZATION/BLINDING

Randomization. This is a cluster-randomized trial, and enrolled patients at a given clinic will receive the intervention assigned to their clinic. A total of 4 primary care clinics in rural Alabama will be randomized to either 1) Receive lifestyle modification alone (DPP) or 2) Receive lifestyle modification with metformin therapy recommendations (DPP-recommendations).

Blinding. Given that this trial is a small pilot randomized at the clinic level and the interventions are very distinct, patients will know their group assignment, as will clinic staff, CHWs, and research staff that are involved in delivering the intervention.

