13 DATA ANALYSIS PLAN

Mixed models will be used to estimate the changes in outcomes by intervention with confidence intervals using practice as a random effect to account for clustering within practices. Secondary models will adjust for baseline values. In 2011, Katula et al. published 12-month results of randomized controlled trial comparing a community-based translation of a DPP lifestyle intervention conducted in a southern sample with usual care. Combined with data generated in our feasibility trial, this relevant study should further help inform our power assessments for a larger RCT. The change values observed in the control group in that project will serve as a reference for expected change in weight without any intervention and will be used to estimate the change due to the intervention.

Handling of Missing Data

Missing data are expected due to dropouts and missed visits. Weight loss is a subject-level variable and missing assessments would influence tests relative to treatment-by-time interactions. The primary analysis described above will employ restricted maximum likelihood using all data. No patients will be deleted from the analysis because of partial data. To assess the sensitivity of results, weight loss will be

analyzed using: 1) all patients irrespective of missing data to perform analysis of variance using mixed effects multi-level models with repeated measures; 2) only patients who have completed all assessment visits and have no missing data, to perform analysis of variance employing mixed effects multi-level models with repeated measures; 3) all patients, irrespective of missing data, to conduct analyses using mixed effects multi-level time trend models with random coefficients to capture individual time trends (does not require complete data across time); and 4) multiple imputation.

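### Section 12's 95% half-widths are single-arm, use patient-level degrees of freedom and take the ICC as known, while Section 13 must estimate the practice variance from four clinics (2 df) and names no small-sample method

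*Combined protocol and SAP*

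**What the plan says.** Section 5 makes the clinic the unit of randomisation: "This is a cluster-randomized trial, and enrolled patients at a given clinic will receive the intervention assigned to their clinic". Section 12 gives the numbers: "We will recruit 25 participants at each of four clinics (2 clinics for each intervention), for a total of 50 per intervention". With one fifth of patients assumed lost, 40 remain in each arm. The section justifies the sample size by feasibility and the precision of estimated changes, and states no power, effect size or arm test.

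Section 12 deals with clustering through a design factor only. The ICC comes from an earlier practice-randomised trial in which "estimated ICCs were <0.01 and not statistically significant". At ICC 0.01 the section gives effective sizes of 40 and 33 per group, and then says body-weight change can be estimated with "95% confidence intervals that are ± 0.28 standard deviations to ± 0.35 standard deviations".

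Section 13 plans mixed models estimated by REML, "using practice as a random effect to account for clustering within practices". It names no denominator degrees-of-freedom method and no correction for a small number of clusters.

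**The concern.** Dividing n by a design factor corrects the standard error for an ICC that is taken as known. It does not allow for having to estimate the between-practice variance. In Section 13 that variance is estimated from four practices, and after one mean per arm only 2 df remain. The two sections therefore describe intervals with different bases, and Section 12 does not say so.

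Precision is the stated reason for this sample size, and the intervals are meant to inform a larger trial. If practices differ more than an ICC of 0.01 implies, intervals that ignore the 2 df will be too narrow and the planning inputs will look firmer than they are. The ICC is borrowed from a trial in people with diabetes, whom Section 4.2 excludes here, and four clinics cannot show whether it carries over. The quoted half-widths also describe one arm's change, although the synopsis and Section 3 present the trial as a comparison of two strategies.

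**Working it through.** **Inputs (Sections 5, 12 and 13).** Four clinics, two per arm; 25 patients per clinic, or 20 after 20% attrition; ICC 0.01; 95% intervals in SD units; REML with practice as a random effect.

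**1. Design factor and effective n.** D = 1 + ICC × (N − 1).
- 25 per clinic: D = 1 + 0.01 × 24 = 1.24; 50/1.24 = 40.3 per arm.
- 20 per clinic: D = 1 + 0.01 × 19 = 1.19; 40/1.19 = 33.6 per arm.

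The plan's D values and effective sizes reproduce.

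**2. The stated half-widths.** One-arm half-width = t(0.975, n − 1)/√n.
- n = 50: 2.010/7.071 = 0.284.
- n = 40.3: 0.319.
- n = 33: 2.037/5.745 = 0.355 (n = 33.6: 0.351).

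The normal quantile gives 0.341 at n = 33, which would round to 0.34, so ±0.35 needs patient-level t. The ±0.28 needs n = 50 with no deflation. At ICC 0.01 throughout, the range is about ±0.32 to ±0.35. An arm difference does not fit the stated range: patient-level t gives 0.40 at n = 50 and 0.49 at n = 33.

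**3. The same standard errors with 2 df.** Practice-level df = 4 clinics − 2 arms = 2, pooling the variance across arms; t = 4.303.
- One arm: 4.303/√40.3 = 0.678; 4.303/√33.6 = 0.742.
- Difference: 4.303 × √(2/40.3) = 0.958; 4.303 × √(2/33.6) = 1.050.

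These are plug-in values, using the true standard error. With 2 df the estimated standard error averages √π/2 = 0.886 of the true one, so the expected half-widths are smaller:
- One arm: 0.886 × 0.678 = 0.60; 0.886 × 0.742 = 0.66.
- Difference: 0.886 × 0.958 = 0.85; 0.886 × 1.050 = 0.93.

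The realised one-arm width varies widely, from about 0.15 to 1.3 SD between the 5th and 95th percentiles.

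**4. Error rate of the interval.** At least 200,000 balanced trials were simulated per setting, with 20 and with 25 patients per clinic. One change value per patient was used, and REML was taken in closed form. ICCs above 0.01 are assumptions, shown for range.

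| ICC | Large-sample REML, variance bounded at zero | 2 df, unbounded variance |
|---|---|---|
| 0 | about 4% | about 5% |
| 0.01 | 5.4–5.8% | about 5% |
| 0.03 | about 8–9% | about 5% |
| 0.05 | about 10–11% | about 5% |
| 0.10 | about 13–14% | about 5% |

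At ICC 0.01 the practice variance is estimated as zero in 55–56% of trials. Replacing the normal quantile by patient-level t helps little: at ICC 0.05 the error is still 9.5–10.5%.

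**The case against.** A reader might infer that the planned analysis cannot deliver the stated precision. The documents do not support that. Section 13 fixes no df method, so 2 df is not part of the plan. At ICC 0.01 a bounded REML fit with a large-sample interval has a median one-arm half-width of 0.29 to 0.33 SD (mean 0.33 to 0.37), close to the stated range, with 5.4–5.8% error. At ICC 0 it is slightly conservative. The only ICC evidence in the documents points to small values; the 8–14% error rates need ICCs that are assumed. All of this stands, and it limits the severity.

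It does not remove the point. Near-nominal coverage depends on an ICC that this trial cannot check, and the reported width depends on an unstated software choice. With a Satterthwaite interval at ICC 0.01, for example, the width rests on 2 df when the practice variance is estimated above zero (44–45% of trials) and on patient-level df otherwise. The median half-width is then 0.31 to 0.34 SD, but the mean is 0.55 to 0.60.

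A reader might also fault the trial for being unable to establish an arm difference. With a 2:2 split there are six allocations, so the smallest two-sided randomisation p-value is 2/6 = 0.33. But Section 12 promises no arm test, and single-arm half-widths fit its stated aim of estimating changes. What follows is only that the arm contrast should be labelled descriptive.

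**Conclusion.** The point holds as a should-fix. Section 12's half-widths are single-arm, rest on patient-level degrees of freedom and treat the ICC as known (0 for ±0.28, 0.01 for ±0.35). Section 13 leaves open how the interval will reflect a practice variance estimated on 2 df.

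At ICC 0.01, a practice-level interval that holds its 5% error would on average be a little under twice as wide as the patient-level one: 0.60/0.319 = 1.9 and 0.66/0.351 = 1.9. The conclusion rests on balanced clinics, variance pooled across arms and one change value per patient. Without pooling there is 1 df per arm (t = 12.71) and the plug-in one-arm half-widths are about ±2.0 to ±2.2 SD. Whether the error of a large-sample interval would in fact exceed nominal depends on an ICC that the documents do not establish for this population and intervention.

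**What to change.** **Section 13.** Prespecify a practice-level small-sample interval. One option is an unbounded practice variance with Kenward-Roger degrees of freedom; the other is an analysis of clinic means with 2 df. The two coincide when clinics are balanced. Attrition may leave clinics unequal, so name one of them in advance. Present the arm contrast as descriptive, without a significance claim.

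**Section 12.** Label the current half-widths as single-arm and conditional on an assumed, known ICC: 0 for ±0.28 and 0.01 for ±0.35. Add the expected 2-df half-widths at ICC 0.01:
- One arm: about ±0.60 to ±0.66 SD on average (plug-in ±0.68 to ±0.74).
- Arm difference: about ±0.85 to ±0.93 SD on average (plug-in ±0.96 to ±1.05).

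State that the realised width will vary widely around these averages.

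**Cost.** Some wording and a model option. The stated and reported precision becomes about half as favourable. No extra patients are needed.
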